- Between the procedure #1 visit and the first exercise visit, participants will be sent home with an ActiWatch Spectrum monitor for activity and sleep.
- Between consent/baseline visit and procedure visit #1, patients will be sent home with a specimen cup with biosafety bag to collect stool and a 3 day dietary log. The log should be collected in real time during a 3 day time period preceding the procedure visit.
- Participants will be asked to collect stool within 72h period (if possible) prior to procedure visit #1 and place sample in a biosafety bag in their home freezer. They will bring the sample to procedure visit and it will be placed immediately in a -80C freezer within the RC2 11th floor lab.

**3. Exercise training.** The exercise intervention will begin at least 24 hours following, and within 14 days of the procedure visit (+/- 14 days for illness, scheduled vacation, etc).

- At the first visit, all participants will repeat physical function testing & 1-RM
- The first 2 weeks will be a lead-in period with low intensity exercise to gain familiarity with the machines. He/she will then be advanced to a moderate intensity exercise for an additional 10 weeks.
- During the exercise training, participants will come to the research center 3 to 4 days/week.
- Chair rise will be measured at the first visit of the week, every 2 weeks and pedometer data will be downloaded.
- To account for unforeseen absences from exercise (due to death of family/friends, illness, etc), the duration of exercise can be extended by up to 4 weeks. This will allow the participant to slowly acclimate back to the prior exercise intensity and minimize risk for injury. The exercise will only be extended if the participant is in agreement. If he/she wishes to complete the exercise intervention within the 24 weeks as planned, then the duration will not be extended.

4. **Acute inflammation visit 1.** At 3 time points during the study, participants will have an “acute exercise visit”.
  - The first will occur during week two of exercise
  - Participants will be asked to exercise on Monday, Thursday, and Friday.
  - **Thursday (beginning between 7:30-10am)** will consist of a high intensity CV + REx exercise stimulus, and a blood draw prior to exercise, and 0, 60, and 90 minutes following an exercise stimulus.

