**2. Exercise testing and training:** All exercise intervention components will include 3 to 4 weekly, supervised sessions of combined CEx + REx at the University of Colorado-Denver (UCD) Exercise Research Laboratory (ERL). All participants will begin with a 2-week supervised, low-intensity exercise acclimation with an experienced research assistant. The initial goal will be to walk on a treadmill for 20-30 continuous minutes at low-intensity (30-40% of maximal aerobic power [VO2max]) and complete 3 sets of 8 repetitions at low-intensity (40-50% of the one-repetition maximum; 1-RM) 3 or 4 days/week. This will facilitate comfort with study equipment and minimize injury.

At 2 weeks, all participants will complete an additional 10 weeks of moderate- intensity exercise, with a goal of 50 minutes of cardiovascular + 3 sets of 8 resistance exercises by the end of the 12 week initial intervention. This will ensure that every participant meets at least the DHHS-PA recommendations in a supervised setting. At week 13, participants will be randomized to continue moderate intensity exercise, or progress to a high-intensity intervention for an additional 12 weeks.

*Maximal aerobic power (VO2 max).* The measurement of VO2max (or peak) will be used to formulate the prescription for CEx at the screening visit. Increases in VO2max in response to exercise training will also verify that the exercise was of sufficient intensity to induce cardiorespiratory adaptations. During an initial 5-min warm-up, walking speed will be adjusted to elicit a HR that is ~70% of maximal HR (from the screening GXT). Speed will then be held constant and the grade of the treadmill will be increased by 2% every 2 minutes until volitional exhaustion or until the test is stopped (see section 4.1.2b). The O2 and CO2 content of expired air will be measured continuously by open circuit spirometry and averaged every 30 sec using an automated online system (TrueMax 2400; ParvoMedics, Sandy, UT). Objective evidence that VO2max has been attained will include at least 2 of the following: a plateau in VO2 despite an increased energy demand, a respiratory exchange ratio in excess of 1.10, and a maximal HR within 10 beats of the age-predicted value. In the absence of these benchmarks, the maximum measured VO2 will be deemed VO2 peak.

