*Muscle strength (1-RM).* Muscle strength will be evaluated as the 1-RM (the maximal weight that can be lifted only 1 time using correct lifting form through the full range of motion) for the upper and lower body REx performed during weeks 1-20. 1RMs will be measured at week 0 and every 4 weeks to week 20. The change in muscle strength from week 0 to 20 will be a secondary outcome measure.

*Exercise intervention.* CEx duration will be increased to 50 minutes of treadmill walking/jogging and exercise intensity will be gradually increased to either 40-50% VO2max (moderate intensity) or 60-70% VO2max (high intensity). By completing 50 minutes of CEx within the 3 weekly visits, we will ensure that all subjects comply with the DHHS guidelines, regardless of their physical activity outside of the routine visits. REx intensity will increase every 2-3 weeks to a target of 3 sets of 8 repetitions at 60-70% of 1-RM (moderate intensity) or >80% of the 1-RM (high intensity).

*Supervised exercise sessions.* Each session will begin with CEx and proceed to REx. Three sets of resistance exercises will include leg press, knee extension, knee flexion, lunges (forward and side), lateral pulldown, chest press, seated row, and dips on a weight-assisted machine. Weight-stack and free weight equipment will be used. Stretching for 10 minutes will conclude each session. Research assistants will supervise exercise, interact frequently with participants, and encourage feedback regarding any discomforts or undue fatigue experienced during or after the exercise sessions. The individualized exercise prescriptions will be geared toward increasing the exercise stimulus while avoiding unfavorable events.

*Physical activity recommendations outside of supervised sessions.* Each participant will be provided with a pedometer (Omron) and recommendations to achieve at least 5,000 steps/day. Walking paths near the participants' home will be mapped for each participant. Information from the NIH Healthy Aging site (exercises for the older adults, nutrition advice, etc) will be provided to each participant at study entry and tip sheets for ways to decrease sedentary time will be provided. Participants will be encouraged to utilize fitness apps (MyFitnessPal, etc) and each subject will receive instructions to partake in physical activity "most" days of the week, outside of their 3x/week supervised sessions.

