Risks: The potential risks of exercise testing and training include development of ventricular arrhythmia, myocardial

infarction, cardiac arrest, and death, as well as the less serious problems of injury to tendons, ligaments, joints, and muscles.

Plans to minimize risk: The risks of exercise testing and training will be minimized by adhering to the following strategies:

**Endpoints for exercise tests:** In asymptomatic individuals who do not develop cardiovascular abnormalities, the endpoint for the maximal exercise tests will be achieving 85% of age-predicted maximal heart rate, fatigue that forces cessation of exercise, or increasingly unstable gait. The criteria that will be used to stop the exercise test before meeting the above criteria include the development of: (a) ST-segment depression of more than 0.2 mV that is either horizontal, downsloping, or slowly upsloping (less than 1 mV/sec) and lasts for 0.08 sec, or ST-segment elevation greater than 0.1 mV; (b) chest pain or discomfort; (c) serious arrhythmias, including multifocal PVCs, ventricular tachycardia, or sustained atrial tachyarrhythmias; (d) development of A-V block or other conduction defects; (e) a fall of systolic blood pressure of 10 mmHg or greater from the peak level with increasing exercise intensity; (f) diastolic blood pressure above 110 mmHg or systolic above 220 mmHg; (g) dizziness; (h) ataxic gait; and (i) pallor or cyanosis. If a subject is noted to have osteoporosis (T-score <-2.5, upon screening, he or she will be referred to their primary care physician to discuss the potential risks and benefits of exercise and the need for immediate or delayed treatment for osteoporosis prior to initiating the study. The risks associated with the muscular strength tests are musculoskeletal pain, fatigue, dizziness, and syncope. These risks will be minimized by providing one-on-one instruction in proper exercise technique on multiple days prior to testing. Workloads will be increased gradually to elicit moderate to maximal effort, and a brief rest period will follow each attempt. Appropriate warm-up and cool-down periods will be included in the strength test procedures. The potential for a serious adverse event to occur with resistance exercise testing is minimal in persons who have undergone prior medical screening. In 20,000 maximal dynamic strength tests in women and men aged 18 to 93 yr, no cardiovascular events were reported [140].

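### The first 1-RM is scheduled at the first exercise visit, with no slot before it for the technique instruction that the protocol promises on multiple days before strength testing

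*Combined protocol and SAP*

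**What the plan says.** Three parts of the combined protocol and SAP bear on this point.

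- **Risk text (IV.D.2, Plans to minimize risk).** It states: "The risks associated with the muscular strength tests are musculoskeletal pain, fatigue, dizziness, and syncope". It then says these risks will be reduced by "providing one-on-one instruction in proper exercise technique on multiple days prior to testing", by raising loads gradually, by resting after each attempt, and by warm-up and cool-down.
- **Visit schedule (IV.C.3, Exercise training).** "At the first visit, all participants will repeat physical function testing & 1-RM". The next item says: "The first 2 weeks will be a lead-in period with low intensity exercise to gain familiarity with the machines". IV.D.2 gives the purpose of this acclimation: "This will facilitate comfort with study equipment and minimize injury". It sets the lead-in resistance load at 40-50% of the 1-RM.
- **Strength measurement (IV.D.2, Muscle strength).** The series starts before any training: "1RMs will be measured at week 0 and every 4 weeks to week 20". Its place among the endpoints is given as follows: "The change in muscle strength from week 0 to 20 will be a secondary outcome measure".

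Two visits come before the first exercise visit. The consent/baseline visit lists history, examination, cognitive screen, ECG, graded exercise test and function tests. Procedure visit #1 lists DXA, vital signs, anthropometrics, blood draw, optional biopsy and questionnaires. Neither lists resistance-technique instruction, and no session is listed between them and the first exercise visit.

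**The concern.** Staff who follow the visit schedule as written would run a maximal strength test before the multi-day instruction that the risk text relies on. Participants are sedentary adults aged 50-75, and the Background section reports that many of those enrolled so far had no experience of weight training. The protocol itself treats familiarity with the equipment as protective, yet places the first 1-RM ahead of it.

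Two things are at stake. The first is musculoskeletal strain in novices. The inflammatory analysis text in section F expects no major injuries and gives muscle strain needing treatment as an example. The second is the strength baseline. If unfamiliarity lowers the first 1-RM, part of the week 0 to 20 change would be practice rather than strength gain. The documents give no figure for such an effect, and none is claimed here.

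**Working it through.** The plan gives no figure to reproduce. The check compares the order of visits and then counts what the conflict and the fix would touch.

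**Order of events as listed**

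1. Consent/baseline visit: no instruction listed.
2. Procedure visit #1: no instruction listed.
3. First exercise visit (week 0): function tests and 1-RM.
4. Two-week supervised lead-in.

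Instruction days listed before the first 1-RM: 0 of 2 visits. Multiple days means at least 2.

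**Can another reading close the gap?**

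- The schedule's word for repeating may cover only the function tests, which are done at the consent/baseline visit. If it also covers the 1-RM, then an unlisted 1-RM came even sooner.
- The lead-in cannot be the promised instruction. Its loads are set from a 1-RM, and counting it as instruction would put the first test after week 2, against both the first visit and week 0.
- Equating week 0 with the first exercise visit is an inference, but any reading of week 0 falls before the lead-in.

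**How many tests are touched**

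- Four-weekly series: weeks 0, 4, 8, 12, 16 and 20 make 6 tests, so the first is 1 of 6.
- Visit schedule: first visit, week 13 and week 23 make 3 tests, so the first is 1 of 3.
- Before a week-4 test there are at least 3 weeks x 3 sessions = 9 supervised sessions. Later tests therefore satisfy the promise.

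**Timing if the 1-RM moves to the third session of week 1** (assumptions: week 1 starts on a Monday, counted as day 1, and sessions are on weekdays)

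- Week-2 acute bout on Thursday = day 11. Current gap: 11 - 1 = 10 days.
- Third session falls Wednesday to Friday = day 3 to 5. New gap: 11 - 3 = 8 down to 11 - 5 = 6 days.
- Delay of the strength baseline: 3 - 1 = 2 to 5 - 1 = 4 days.
- Next two-weekly chair rise = day 15, which is 15 - 5 = 10 to 15 - 3 = 12 days after the test.
- Sessions in the two lead-in weeks: 3 to 4 in week 1 plus 3 in week 2 (Monday, Thursday, Friday, including the acute bout) = 6 to 7. Two of these would not be loaded by % 1-RM: 2/7 = 29% to 2/6 = 33%.

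**The case against.** The strongest reply is that the visit lists in IV.C are not exhaustive. Section IV.D contains procedures with no matching visit entry: HIV antibody testing, the week-14 fasting draw, the 24-hour post-exercise sample, the activity questionnaire at weeks 4, 8, 16 and 20, and the four-weekly 1-RMs themselves. The technique instruction could be another such item. This stands, and it rules out a stronger inference that a reader might draw: that every enrolled participant would be tested without instruction. The documents show a missing slot, not a missing safeguard.

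A reader might also infer that a maximal lift is each participant's first contact with the machines. The risk text does not support that. Loads rise gradually within the test, with warm-up and rests, and medical screening with a monitored exercise test comes earlier. The remark about inexperience also comes from early conversations with enrolled participants, when the text describes 15 HIV-infected enrollees, so it does not establish the same for the HIV-negative controls.

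The protocol offers further reassurance: "In 20,000 maximal dynamic strength tests in women and men aged 18 to 93 yr, no cardiovascular events were reported". That is relevant to cardiac risk but does not address strain.

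On measurement, a practice effect of similar size in both HIV groups (an assumption) would largely cancel in the between-group comparison of strength change, though not in the within-group change.

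The reply does not remove the sequence itself. Supervised exercise sessions start at the very visit where the first 1-RM is placed, so a literal reading of the schedule puts the test ahead of the instruction.

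**Conclusion.** The point holds as a minor, cheaply corrected inconsistency. The promised instruction has no place in the schedule before the first 1-RM, and later 1-RMs are unaffected.

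The reach is narrow: one test per participant and the secondary strength-change outcome. Nothing here supports a claim of bias in the primary chair-rise outcome. The randomised intensity comparison begins at week 13, where the visit schedule has its own 1-RM. The size of any practice effect is unknown.

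The conclusion does not depend on which of the two 1-RM calendars is followed, because both put the first test before the lead-in training. The day counts do depend on the assumed Monday start.

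**What to change.** - Keep function testing at the first exercise visit.
- Use the first two supervised sessions of week 1 for one-on-one technique instruction at light loads guided by perceived effort.
- Take the baseline 1-RM at the third session of week 1.
- Set the remaining lead-in loads and the week-2 acute bout from that result.

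Delaying the test to the end of the lead-in would work less well, because the week-2 high-intensity bout would then have no 1-RM to be set from.

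The change needs revised wording in IV.C.3 and in the Muscle strength paragraph of IV.D.2, and a re-ordering of sessions already planned. It adds no visit. The baseline blood draw, biopsy and week of activity monitoring all come before the first session and are untouched.

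The costs are small: two of the 6 to 7 sessions in the lead-in weeks are not loaded by % 1-RM, the strength baseline comes 2 to 4 days later and after some light exercise, and the maximal test sits 6 to 8 days rather than 10 before the week-2 bout.

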  - Participants will be encouraged to avoid a large meal before exercise (snack is ok and encouraged). Blood pressure will be monitored before exercise, after the CVEx, and after the REx. As the expected response to exercise would be an increase in blood pressure, the PI will be contacted for any decreases in blood pressure after exercise.
5. **Week 12.**
  - Full physical function, anthropomorphics, questionnaires will be administered on Monday of week 12
  - The **Acute Inflammation visit 2** will occur on Thursday morning of week 12 (**beginning between 7:30-10am**). Arrangements for alternative dates can be made, but the participant must have at least 48 hrs from the prior exercise session). Participants will be encouraged to avoid a large meal before exercise (snack is ok and encouraged). Blood pressure will be monitored before exercise, after the CVEx, and after the REx. As the expected response to exercise would be an increase in blood pressure, the PI will be contacted for any decreases in blood pressure after exercise.
6. **Randomization/Week 13 visit.** At week 13, participants remaining on study will be randomized to either continue moderate intensity or advance to a higher-intensity exercise regimen with the randomization sequence generated by the study statistician ([name]).
  - V02, 1-RM will be measured on Monday of this week to develop a new prescription.
7. **Week 23.**
  - V02, 1-RM will be measured between Wed-Friday of this week.
8. **Week 24.**
  - **Acute inflammation visit 3.** During the week 24 of exercise, participants will be asked to exercise on Monday, Thursday, and Friday.
  - **Thursday (between 7:30-10 am)** will consist of a high intensity CV + REx exercise stimulus, and a blood draw prior to, and 0, 60, and 90 minutes following an exercise stimulus. Participants will be encouraged to avoid a large meal before exercise (snack is ok and encouraged). Blood pressure will be monitored before exercise, after the CVEx, and after the REx. As the expected response to exercise would be an increase in blood pressure, the PI will be contacted for any decreases in blood pressure after exercise.
  - Full physical function testing will occur on the final day of the exercise intervention
9. **Procedure visit #2.** Participants will return >48 hours after the last exercise session for a 2nd procedure visit for muscle biopsy (n=36), DXA scan, and blood draw.
  - DXA
  - Fasting for muscle biopsy (n=36)

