## **5. Venipuncture:**

Laboratory analyses will include: CBC, CMP at procedure visit #1 only.

HIV antibody for participants that are not known to be HIV+ if no HIV testing available within the past 1 year.

Fasting IGF-I, IGF-BP3, total/free testosterone, IL-6, sTNFRI and sTNFRII, insulin and glucose will be evaluated at procedure visits #1 and #2, and at week 14, at least 48 hours following the last exercise session.

Inflammatory markers (IL-6, sTNFR-1, and TNF-alpha) will be measured pre-exercise, and 0, 60, or 90 minutes, and ~ 24 hours after a high-intensity exercise stimulus at week 2, 12, and 24.

For the optional microbiome substudy, EDTA plasma samples will be assessed for LPS, heparin plasma samples for sCD14, iFABP) and CRP. LPS levels will be measured using the Limulus Amebocyte Lysate (LAL) assay (Lonza, Switzerland) with plasma samples diluted 1:10 in endotoxin free water and heat-inactivated at 80°C for 15min. Commercially available ELISAs will be used to evaluate levels of IL-6, sCD14, and iFABP (all R&D Systems, Minneapolis, MN). Serum LBP levels were assessed using a custom ELISA all as reported in Dillon 2014.

Peripheral blood mononuclear cells (PBMCs) will be collected at each of the pre-exercise acute visits (weeks 2, 12, and 24) and stored. Future analyses (pending funding) will include an assessment of markers of T-cell and B-cell activation

Samples will be stored for additional analyses. These assays will be performed from stored specimens (in batch to minimize inter-assay variability) in the Clinical Translational Research Center (CTRC) core laboratory at UCD or by [name] in [name] laboratory. **All participant samples will be drawn between 7:30-10am. We will draw approximately 70 mL at the initial visit and 75 mL at the subsequent 3 visits.**

Risk: There is a small risk of local hematoma or infection associated with blood sampling.

Plans to minimize risk: The risks of hematoma and infection are minimized by having trained clinical personnel perform the procedures using sterile techniques.

Justification: We will be evaluating the response of HIV+ vs HIV- individuals to an exercise intervention, in hormone levels and markers of inflammation. Additional samples will be collected for storage. These safety and efficacy markers will be imperative in the design of future, larger intervention studies of exercise in HIV.

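### The final function battery falls about a day after the week-24 high-intensity bout, whereas the week-12 battery precedes its bout; residual fatigue could favour the high-intensity arm, mainly on the secondary measures

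*Combined protocol and SAP*

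**What the plan says.** Section IV.C item 8 (Week 24) states "During the week 24 of exercise, participants will be asked to exercise on Monday, Thursday, and Friday". The Thursday session "will consist of a high intensity CV + REx exercise stimulus, and a blood draw prior to, and 0, 60, and 90 minutes" after the stimulus, and it applies to both arms. The same item adds that "Full physical function testing will occur on the final day of the exercise intervention". Section IV.D.5 (Venipuncture) includes a blood sample about "24 hours after a high-intensity exercise stimulus at week 2, 12, and 24", which fits a Friday visit.

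The week-12 arrangement (section IV.C item 5) differs: "Full physical function, anthropomorphics, questionnaires will be administered on Monday of week 12", with that week's acute bout on Thursday. If the week-12 acute visit is moved to another date, "the participant must have at least 48 hrs from the prior exercise session". No rest interval, and no order of testing and exercise, is given for the final function battery.

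Section IV.D.2 sets the resistance targets at "60-70% of 1-RM (moderate intensity) or >80% of the 1-RM (high intensity") and the cardiovascular targets at 40-50% versus 60-70% of VO2max. Everyone trains at moderate intensity up to week 12; the arms separate at week 13.

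For the primary outcome, section IV.C item 3 says "Chair rise will be measured at the first visit of the week, every 2 weeks". Section IV.F confirms that chair rise is bi-weekly and that the other functional measures are taken three times. It plans a linear mixed model of change from week 0 with a group-by-time term.

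**The concern.** The final battery is taken under different recovery conditions from the week-12 battery, and the difference may not be equal between the randomised arms. In weeks 13 to 24 the high arm trains routinely at the upper intensity and the moderate arm does not. The Thursday bout is therefore further from usual training for the moderate arm. The resistance exercises include leg press, knee extension and lunges, which load the muscles that chair rise, stair climb and the 400-m walk depend on.

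If the moderate arm is slower on Friday for this reason, high intensity looks better than it is, which is the direction of Hypothesis 1b. The effect arises after randomisation, so balance at allocation does not remove it. Once the data are collected it cannot be separated from a training effect, because each final-day value carries it. Section IV.F does not mention the timing.

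**Working it through.** **1. Timing of each function test relative to the acute bout**

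| Test | Day | Relation to the acute bout |
|---|---|---|
| Full battery, week 12 (IV.C item 5) | Monday | Before Thursday's bout |
| Bi-weekly chair rise (IV.C item 3) | First visit of the week | Before any Thursday bout |
| Full battery, final (IV.C item 8) | Last day of the intervention; Friday by inference | About 24 hours after Thursday's bout |

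Only the final battery follows the bout.

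**2. The plan's own power figure.** Inputs from section IV.F: 29 per group, difference 1.5 s, SD 2.0 s, two-sided 0.05, two-sample t-test.
- SE = 2.0 × √(2/29) = 0.525 s
- Noncentrality = 1.5/0.525 = 2.86; df = 56
- Power = 80.1%, which agrees with the plan's statement of over 80%.

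**3. Worst case: a stand-alone contrast of the final-day values.** Let b be the extra slowing of the moderate arm. The documents give no value, so b is an assumption. With no true effect, the chance of significance favouring high intensity comes from the noncentral t with noncentrality b/0.525.

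| Assumed b | b as share of 1.5 s | b/SE | Chance of significance favouring high intensity |
|---|---|---|---|
| 0 | 0% | 0 | 2.5% |
| 0.25 s | 17% | 0.48 | 6.8% |
| 0.50 s | 33% | 0.95 | 15.3% |
| 0.75 s | 50% | 1.43 | 28.9% |

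**4. How much of b reaches a chair-rise analysis that uses repeated measures.** Take the final-day value as the only week-24 value, two-weekly tests, unweighted least squares, and no within-person correlation.
- Linear slope, weeks 0 to 24 (13 tests, mean week 12, sum of squares 728): weight on the 24-week change = 24 × 12/728 = 0.40.
- Linear slope, weeks 12 to 24 (7 tests, mean week 18, sum of squares 112): weight on the 12-week change = 12 × 6/112 = 0.64.
- Average of the six tests at weeks 14 to 24: weight = 1/6 = 0.17.

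Holding the SE at 0.525 s, for illustration only, the chance of significance favouring high intensity becomes:

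| Assumed b | Slope, weeks 0-24 | Slope, weeks 12-24 | Average, weeks 14-24 |
|---|---|---|---|
| 0.50 s | 5.6% | 8.7% | 3.6% |
| 0.75 s | 8.0% | 14.5% | 4.2% |

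A model-based SE would differ from 0.525 s. A smaller one would make the same bias more costly.

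**5. Measures with three time points.** The 4-m and 400-m walks, stair climb, grip and balance have one final value each. For these measures no bi-weekly series dilutes b, and no pre-bout value exists in week 24.

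**The case against.** A reader might infer that the primary test of Hypothesis 1b is biased towards high intensity, with false-positive rates of 7% to 29%. The documents do not support that, for four reasons.

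- **Chair rise is probably protected already.** Counted two-weekly from week 0, the first-visit-of-the-week test yields a week-24 value before the bout. What is missing is a statement of which week-24 value counts.
- **The planned analysis is not a single-visit t-test.** The mixed model uses all time points. The 7%, 15% and 29% figures would need a model with categorical time, tested at week 24 on the final-day value alone.
- **The size of b has no source.** Zero is as compatible with the documents as 0.75 s.
- **The direction is not established.** Both arms have acute bouts at weeks 2 and 12 and strength and VO2 testing in week 23, so the moderate arm is not new to hard effort. The load of the acute bout is not defined beyond being high intensity. The high arm trains harder throughout weeks 13 to 24 and could carry more cumulative fatigue. The Background section links muscle damage from high-intensity exercise to certain conditions such as heightened inflammation, not to training history.

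A reader might also infer bias in the HIV comparison. Section IV.F balances intensity within HIV status (18 moderate and 18 high in each group), so that contrast is largely protected. A difference in recovery by HIV status would be speculation.

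The timing itself rests on inference. Friday is not named, the intervention may be extended by up to 4 weeks, and section IV.D.4 places the functional measures at entry, week 10 and visit 20. Nor is baseline clearly a rested state: at the consent visit, function testing is listed after a graded exercise test.

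These points remove the case for a serious threat to the primary outcome. They leave in place the unequal timing of the week-12 and final batteries, the absence of a rest rule, and the exposure of the measures with a single final value.

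**Conclusion.** The point holds in a limited form. Followed as written, section IV.C puts the final battery about 24 hours after a high-intensity bout, while the week-12 battery comes before its bout. The two arms differ in how far that bout departs from their usual training, so a bias favouring Hypothesis 1b is possible. Its size is unknown, and its direction is plausible rather than shown.

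The exposure is mainly in the secondary measures with three time points. For chair rise it arises only if the final-day value is taken as week 24, and then roughly 0.17 to 0.64 of the bias reaches a slope or averaged estimate. The conclusion assumes that the last listed session is the final day and that section IV.C, not IV.D.4, governs the schedule. It merits a low-cost correction and does not call the primary analysis into question.

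**What to change.** - In section IV.C item 8, move the final full function battery to Monday of week 24, before that day's session and before the acute bout, as at week 12. The strength and VO2 tests fall on Wednesday to Friday of week 23, so they would precede it by about three days or more.
- State in section IV.F that the first-visit-of-the-week chair rise is the week-24 value, and that a final-day value after the acute bout is not used in its place.
- Reconcile section IV.D.4 (entry, week 10, visit 20) with section IV.C (week 12 and the final day), so that one schedule governs the functional measures.

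The cost is one line in the visit schedule and one in the analysis plan, with no new visit, test or staff. The drawback is that the final test precedes the last two or three training sessions.
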